9.9 Development safety update reports

Within 60 days following the anniversary of the authorisation date for the trial, a Development Safety Update Reports (DSURs) will be sent by the Chief Investigator to the MHRA and the Main Research Ethics Committee. A copy of the report will also be sent to GSK (as the trial funder/drug supplier), the University of Leicester (as the trial Sponsor), and all host organisations. The LCTU will prepare the DSUR report on behalf of the CI and submit to the Sponsor who is responsible for reporting to the Competent Authority (MHRA) within the specified time frame.

10 STATISTICS AND DATA ANALYSIS

10.1 Sample size calculation

Readmission rates at 6, 9 and 12 months were 51%, 59% and 64% respectively for patients admitted with a diagnosis of COPD (ICD code: J44) in Leicestershire in 2015. This is in line with national data from the HQIP RCP National COPD audit (2014) which had a readmission rate of 43% at 3 months. In addition, 6% of patients discharged from hospital with an exacerbation of COPD died in the 12 months following admission without hospital readmission.

National UK data from the HQIP funded RCP/BTS National COPD audit (2014; data unpublished) showed 24.9% patients had an eosinophil count of ≥ 300 cells/ μL on admission. In patients with an eosinophil of ≥ 300 cells/ μL on admission ($n=1,587$), 46.1% of patients were readmitted within 3 months of initial hospitalisation, similar to the non-eosinophilic COPD population.

Assuming 65% of patients receiving usual care will have an event by 48 weeks (composite endpoint: hospitalisation or death) and those treated with mepolizumab have a hazard ratio of 0.6, then 226 patients (113 per group) would be required to show a statistical difference power 0.8, $\alpha=0.05$). We have also assumed 5% drop-out (recruited but not receiving first dose) and therefore the final recruitment target of 238 patients.

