4.1 Truncated follow-up

Participants randomised from July 2023 to December 2023 will be consented to a truncated follow-up model, whereby the timing of the last participant last visit will remain on the same timeline as originally planned; this will result in participants consented in July to have up to the 44-week follow-up, those in August will have up to the 40-week follow-up, and so on. Participants will be dosed for a minimum of 20 weeks (participants will be dosed at baseline, therefore all participants will receive at least 6 doses), with secondary outcomes measured as per original timelines (baseline, 4 weeks, 8 weeks, etc.) however final outcome measures normally measured at 48 weeks will occur at 4 weeks \pm 7 days post final dosing visit.

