10.7 Participant population

The primary analysis for each efficacy outcome will be by 'intention to treat' analysis; all the participants randomised in to the trial (regardless of whether they received trial drug) will be analysed in their allocated group. Outcome data obtained from all participants will be included in the data analysis. The primary analysis of safety outcomes will be analysed using the safety population. The safety population will be comprised of the all individuals that received at least one injection of either the active dose or the placebo, with individuals that received any injections of the active dose being in the mepolizumab arm.

Some of the secondary outcomes i.e. number of hospital readmissions and number of moderate exacerbations over 48 weeks, will be analysed on the per-protocol population where patients will be included in the analysis if they have a received a minimum duration of trial treatment of 24 weeks.

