2.2.3 Sample size

Readmission rates at 6, 9 and 12 months were 51%, 59% and 64% respectively for patients admitted with a diagnosis of COPD (ICD code: J44) in Leicestershire in 2015. This is in line with national data from the HQIP RCP National COPD audit (2014) which had a readmission rate of 43% at 3 months. In addition, 6% of patients discharged from hospital with an exacerbation of COPD died in the 12 months following admission without hospital readmission.

National UK data from the HQIP funded RCP/BTS National COPD audit (2014; data unpublished) showed 24.9% patients had an eosinophil count of ≥ 300 cells/ μL on admission. In patients with an eosinophil of ≥ 300 cells/ μL on admission ($n=1,587$), 46.1% of patients were readmitted within 3 months of initial hospitalisation, similar to the non-eosinophilic COPD population.

Assuming 65% of patients receiving usual care will have an event by 48 weeks (composite endpoint: hospitalisation or death) and those treated with mepolizumab have a hazard ratio of 0.6, then 226 patients (113 per group) would be required to show a statistical difference power 0.8, $\alpha=0.05$). We have also assumed 5% drop-out (recruited but not receiving first dose) and therefore the final recruitment target of 238 patients.

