6.4 Primary Outcome Analysis

6.4.1 Primary Analysis of Primary Outcomes

The primary analysis will take place on the intention to treat population. All participants will be included in the model using censored values for participants not experiencing an event during their follow-up period.

The primary analysis will fit the Cox proportional hazard model for the primary outcome of the time to re-hospitalisation or death (any cause) as the dependent variable, treatment group as an explanatory factor and baseline MRC dyspnoea score (≤ 3 , > 3) and past hospitalisation in the previous 12 months ($(0, \geq 1)$) (Stratification factors). This analysis will be accompanied by Kaplan-Meier survival curves alongside with log rank test to compare the survival rate between the two groups. A hazard ratio (HR) of the mepolizumab relative to placebo, with their associated two-sided 95% confidence interval and p-values will be reported. A p-value ≤ 0.05 will be considered as significant difference.

Time until event (re-hospitalisation or death from any cause) will be measured in days from randomisation until re-hospitalisation, death or 12-month follow-up assessment, whichever happens first. Participants with no event (no re-hospitalisation or alive) assessed during follow-up visits will be censored at the last assessment date free from event.

Participants who do not complete the 12-month follow-up will be included in the primary analysis; those without a recorded event will be censored. Participants who withdraw from the trial will be censored at the date of withdrawal and participants lost to follow up will be censored at the date last assessment.

Proportional hazard assumption for the Cox proportional hazard model will be checked using the statistical tests and graphical diagnostics based on the Schoenfeld residuals.

Where participants don't reach the 12 month assessment but do not experience an event the last date of assessment known to be event-free will be used as the censor

value (right censoring). This will apply to participants who are withdrawn and/or lost to follow-up for any reason or receive truncated follow-up as part of the revised protocol. In the event of encountering multiple events occurring at the same time t , Efron's method for dealing with tied survival times will be implemented when fitting the Cox model to the data.

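### The stated power of 0.8 describes 226 dosed patients followed for 48 weeks, not the 238-patient ITT analysis with truncated follow-up; restated, it is somewhat below 0.8 on most readings

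*Protocol*

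**What the plan says.** The sample size text is the same in Protocol 10.1 and SAP 2.2.3.

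- Control risk: "Assuming 65% of patients receiving usual care will have an event by 48 weeks".
- Effect: "those treated with mepolizumab have a hazard ratio of 0.6".
- Size: "then 226 patients (113 per group) would be required to show a statistical difference power 0.8", with alpha 0.05.
- Inflation: "We have also assumed 5% drop-out (recruited but not receiving first dose) and therefore the final recruitment target of 238 patients".

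Other sections describe a different analysis set and a different follow-up.

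- Protocol 10.7, repeated in SAP 4.2, defines the primary efficacy set: "all the participants randomised in to the trial (regardless of whether they received trial drug) will be analysed in their allocated group".
- Protocol 4.1, repeated in SAP 2.1, shortens follow-up for July to December 2023 entrants: "participants consented in July to have up to the 44-week follow-up, those in August will have up to the 40-week follow-up, and so on". The minimum is 24 weeks.
- SAP 6.4.1 right-censors these participants at their last event-free assessment. Protocol 10.3.2 censors withdrawals at the withdrawal date.

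Neither document gives the number truncated, the hazard or follow-up assumed for the never-dosed, or a revised power.

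**The concern.** Two parts of the calculation do not match the current design.

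- **Analysis set.** Dividing by 0.95 is right if the 5% contribute nothing to the analysis. Under ITT they are analysed. If those in the mepolizumab arm are followed without treatment, they carry the control hazard and pull the hazard ratio towards 1. Adding patients in proportion does not fully repair that.
- **Follow-up.** The 65% applies to 48 weeks in everyone. Participants censored at 24 to 44 weeks yield fewer events.

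Both effects lower power, and the stated design has almost no slack. If the sentence is carried into the trial report, a null result would be read against a power that the current design was never shown to have.

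**Working it through.** **Inputs from the documents.** Control risk 65% at 48 weeks, HR 0.6, 1:1 allocation, 5% never dosed, N = 238. The sample size sentence does not state sidedness; SAP 6.4.1 reports a two-sided interval, so two-sided 0.05 is used.

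**Inputs assumed.**
- Number truncated. Protocol 10.2 supports two values: 469 × 50% / 36 months = 6.5 a month, or 39 in six months; its stated 13 a month gives 78. They are spread equally over 44, 40, 36, 32, 28 and 24 weeks.
- Event curve. Either a constant hazard, or a front-loaded curve through the readmission figures in Protocol 10.1 (43%, 51%, 59%, 64% at 3, 6, 9, 12 months) rescaled to 65% at 48 weeks.

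**1. Reproduce the plan.**
- Mepolizumab risk = 1 − 0.35^0.6 = 0.467; mean risk = (0.65 + 0.467)/2 = 0.5587.
- Freedman events = (1.960 + 0.842)² × (1.6/0.4)² = 125.6, so 126.
- N = 126/0.5587 = 225.5, so 113 per group, 226 in all. This matches.
- 226/0.95 = 237.9, so 238. This matches.
- Schoenfeld would give 217–218 and one-sided Freedman about 178, so the plan's method is two-sided Freedman.

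**2. Power formulas, for E events.**
- Freedman: Φ(√E × (1 − HR)/(1 + HR) − 1.960).
- Schoenfeld: Φ(√E × |ln HR|/2 − 1.960).

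**3. Dilution, if the never-dosed are followed at the control hazard.** The effective HR depends on how it is averaged:
- log scale: 0.6^0.95 = 0.6155;
- cumulative hazard at 48 weeks: ln(0.5235)/ln(0.35) = 0.6165;
- average initial hazard: 0.95 × 0.6 + 0.05 × 1 = 0.62.

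Expected events with no truncation: mepolizumab risk 0.95 × 0.467 + 0.05 × 0.65 = 0.4765, so 119 × (0.65 + 0.4765) = 134.1.

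**4. Results.** Ranges cover the two event curves and, where dilution applies, the three effective HRs. Simulation is a log-rank test with 20,000 runs per setting.

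| Design | Truncated | Events | Freedman % | Schoenfeld % | Simulation % |
|---|---|---|---|---|---|
| 226, all 48 weeks (as stated) | 0 | 126.3 | 80.2 | 81.9 | 81.3–81.5 |
| 238, no dilution | 39 | 128.3–130.5 | 80.8–81.5 | 82.5–83.1 | 82.6–82.9 (40 truncated) |
| 238, never-dosed at control hazard | 0 | 134.1 | 77.5–78.7 | 79.0–80.2 | 79.6–80.1 |
| 238, never-dosed at control hazard | 39 | 129.3–131.6 | 76.0–77.9 | 77.6–79.5 | 77.8–78.6 |
| 238, never-dosed at control hazard | 78 | 124.6–129.1 | 74.5–77.2 | 76.1–78.7 | 76.1–78.2 |
| 226 informative, never-dosed censored at once | 37–39 | 121.6–123.9 | 78.7–79.5 | 80.4–81.1 | 80.0–81.2 |
| 226 informative, never-dosed censored at once | 74 | 117.4–121.6 | 77.3–78.7 | 79.0–80.4 | 78.6–80.1 |

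Withdrawal after dosing is not included. It has no allowance in the plan and would lower every row except the first.

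**The case against.** The strongest case against is that nothing was miscalculated and that 80% lies within the range of defensible answers.

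- **The never-dosed may not be followed.** Protocol 7.8 withdraws those who decline further data collection, and Protocol 10.3.2 censors them at that date. For them, dividing by 0.95 is right. This stands as a possible reading. However, Protocol 7.8 asks those who stop treatment for at least admissions and deaths, and Protocol 7.11 follows those lost through hospital records, so the plan aims for follow-up. Even with immediate withdrawal, Freedman's formula falls just short of 80% once about 39 are truncated.
- **Freedman is conservative here.** This stands: simulation gives 81.3–81.5% for the stated design. Compared like with like, simulation still falls by about 3 points with dilution and 39 truncated.
- **The cited data exceed 65%.** Readmission interpolated to 48 weeks is 59 + 5 × 9/13 = 62.5%, and deaths without readmission add 6 × 48/52 = 5.5%, about 68% together. With 68%, dilution and truncation, Freedman gives 79.0–79.8%. This stands as mitigation, but the plan states 65%.
- **The gap hardly matters.** Power is given to one decimal, recruitment was due to end in December 2023, and the result will be read from the hazard ratio and its interval. This limits the importance; it does not make the sentence describe the design.

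A reader might infer that the design delivers a fixed 77–78%. The documents do not support so exact a figure, because the number truncated and the fate of the never-dosed are not given. A reader might also infer that truncation by itself broke the power; about 39 truncated with no dilution leaves about 81%.

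**Conclusion.** The point holds as a mismatch between the stated power and the current design, not as an error of arithmetic. The power of 0.8 belongs to 226 dosed patients with 48 weeks each.

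At 65% control events and HR 0.6, with about 39 truncated, the plan's own formula misses 0.8 on either reading of the never-dosed: by about 2 to 4 points if they are followed at the control hazard, and by about 0.5 to 1.5 points if they are censored at once. Schoenfeld and simulation give a shortfall of about 0.5 to 2.5 points on the first reading and none on the second. With 78 truncated and the never-dosed followed, Freedman falls to about 74.5–77%.

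Dilution by the never-dosed is the main cause. The sizes rest on the assumed number truncated, the hazard and follow-up of the never-dosed, and the shape of the event curve. The documents settle none of these, so a single replacement figure cannot be stated from them.

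**What to change.** In Protocol 10.1 and SAP 2.2.3:

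1. Keep the existing calculation, labelled as the a priori basis for 226 and 238, and name the method (Freedman, two-sided).
2. Add expected events and power for 238 participants analysed by ITT, using the actual number truncated with their follow-up lengths, a stated assumption for the never-dosed (followed at HR 1, or censored early) and expected withdrawal.
3. Give that result as the design's power in place of 0.8.
4. Reword the drop-out sentence so that it no longer implies that the 5% are outside the primary analysis.

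The cost is a short addition to one section of each document and a slightly less favourable stated power. No extra patients and no change to the analysis are needed.

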10.2 Planned recruitment rate

Recruitment will be over a 3-year period. Admission rates are increasing year-on-year therefore we would expect a minimum 1,953 patients admitted with COPD over this time. Eosinophil count was collected as part of the National COPD audit, where 24% of patients had an eosinophil count of $\geq 0.3 \times 10^9$. Therefore, it is anticipated that at least 469 patients will be hospitalised with an eosinophilic exacerbation of COPD. Based on recruitment of 50% of these patients, then a recruitment target of 13 per month would be expected.

10.3 Statistical analysis plan

A separate, version controlled Statistical Analysis Plan (SAP) will contain full details of all statistical analyses and an initial version prepared prior to the first DSMC. Modifications made to the SAP during the conduct of the trial will be detailed in a summary of changes table with the reason(s) for their change in subsequent statistical analysis plans versions.

Reporting of results will be based on the CONSORT statement. A Trial Steering Committee and Data Monitoring Committee will be established, with appropriate charters that will specify the remit.

A total of 238 participants will be randomised in a 1:1 ratio to receive mepolizumab or a matching placebo. For safety and tolerability, AEs, SAEs, vital signs, physical examinations, ECGs and clinical laboratory assessment at specific time points will be evaluated. All safety data will be summarised descriptively. Number and percentage of AEs will be presented for each treatment by preferred AE term and system organ class of the current Medical Dictionary for Regulatory Authorities (MedDRA) dictionary.

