2.1 Assessment and management of risk

Mepolizumab is licensed and used clinically for severe asthma. It has been utilised in two randomised controlled trials in COPD comprising 865 patients in the treatment arms. The overall safety profile is good with no difference in reported side effects between treatment and placebo. The most common reported side effect is headaches (>1 in 10), followed by local injection site reactions expected in 3-8% of the population, similar in placebo and active drug (Pavord et al. 2017; Papi et al. 2018).

Beyond standard of care, the participants will undergo additional blood tests, breathing tests, airway sampling, urine tests, faeces sampling, and a subcutaneous IMP. These are all common routine tests. The blood, breath and airway sampling has minimal risk and mild discomfort. We will also monitor and analyse all potential cases of anaphylaxis and major adverse cardiac events (MACE).

This trial is categorised as:

- Type B = somewhat higher than the risk of standard medical care

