4.5 Safety Population

The primary analysis of safety outcomes will be analysed using the safety population. The safety population will be comprised of the all individuals that received at least one injection of either the active dose or the placebo, with individuals that received any injections of the active dose being in the mepolizumab arm.

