6.8 Changes to the Planned Analysis

None.

7 Safety and Adverse events

All safety data will be presented according to the Safety population.

All adverse events will be listed including characteristics such as seriousness, duration, relatedness, severity, action taken and outcome.

Adverse events' frequencies by seriousness, relatedness and severity will be summarised by treatment group and overall.

Adverse events frequencies will also be presented by treatment arm for each MedDRA Coding system organ class observed.

Graphical illustrations of frequencies by arm in total and by system organ class will be presented.

Furthermore, AE and SAE event rates will be reported as incidence rates per person years and calculated as (total number of events / sum of all follow-up times) *52 where;

- Total number of events is a count of all AE/SAEs observed.

- Follow-up time is calculated per participant from time of first dose until the last trial assessment is recorded.

8 References

Dodd, J. W., Hogg, L., Nolan, J., Jefford, H., Grant, A., Lord, V., ... Hopkinson, N. S. (2011). The COPD Assessment Test (CAT) - Response To Pulmonary Rehabilitation. A Multicentre, Prospective Study. *Thorax*, 66, 425–429.

Muller, J. P., Gonçalves, P. A., Fontoura, F. F., Mattiello, R., & Florian, J. (2013). Applicability of the London Chest Activity of Daily Living scale in patients on the waiting list for lung transplantation. *Jornal brasileiro de pneumologia : publicacao oficial da Sociedade Brasileira de Pneumologia e Tisiologia*, 39(1), 92–97.

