9.1 Appendix 1: Templates for Tables, Listings and Figures

Table1: Disposition of Patients by treatment arm

	Control, n (%)	Mepolizumab, n (%)	Total, n (%)
Randomised patients			
Completed trial follow-up (End of trial assessment)			
Discontinued due to			
Lost to follow-up			
Withdrawn			
Deaths			
Remained on treatment for intended follow-up period			
Discontinued treatment early			
Reasons:			
Participant decision			
Adverse Event			
Unable to Tolerate Drug			
Participant non-compliance			
Lost to Follow up			
Investigator decision			
Participant Ineligible			
Withdrawn due to Medical Reasons			
Death			
Number of doses received			
1			
2			
3			
4			
5			
6			
7			
8			
9			
10			
11			
12			

Figure 1: A Swimmer plot of participants' discontinuation from the trial with reasons

Table 1: Case Report Form (CRF) return

CRF	Placebo Returned/Expected (%)	Mepolizumab
Visit 1 (Week 0)	Follow-up due	
	Follow-up completed	
Visit 2 (Week 4)	Follow-up due ^a	
	Follow-up completed	
Visit 3 (Week 8)	Follow-up due ^a	
	Follow-up completed	
Visit 4 (Week 12)	Follow-up due ^a	
	Follow-up completed	
Visit 5 (Week 16)	Follow-up due ^a	
	Follow-up completed	
Visit 6 (Week 20)	Follow-up due ^a	
	Follow-up completed	
Visit 7 (Week 24)	Follow-up due ^a	
	Follow-up completed	
Visit 8 (Week 28)	Follow-up due ^a	
	Follow-up completed	
Visit 9 (Week 32)	Follow-up due ^a	
	Follow-up completed	
Visit 10 (Week 36)	Follow-up due ^a	
	Follow-up completed	
Visit 11 (Week 40)	Follow-up due ^a	
	Follow-up completed	
Visit 12 (Week 44)	Follow-up due ^a	
	Follow-up completed	
Visit 13 (Week 48)	Follow-up due ^a	
	Follow-up completed	

^a Will be defined as participants who have passed the visit window stated in the Protocol.

Table 2: Demographic and Baseline Clinical Characteristics

Characteristics	Descriptive	Placebo (n=)	Mepolizumab (n=)	Total (n=)
Age	N			
	Mean [SD]			
	Median [IQR]			
	Min, Max			
Gender	Male			
	Female			

Ethnicity	White
	Asian or Asian British
Smoking status	Current Smoker
	Ex-Smoker
BMI	N
	Mean [SD]
	Median [IQR]
	Min, Max
Number of cigarettes per day	N
	Mean [SD]
	Median [IQR]
	Min, Max
Number of years smoked	N
	Mean [SD]
	Median [IQR]
	Min, Max
Number of emergency admissions (all cause) in previous 12 months	N
	Mean [SD]
	Median [IQR]
	Min, Max
Number of courses of steroids without antibiotics for your chest (COPD exacerbations) in previous 12 months	N
	Mean [SD]
	Median [IQR]

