	KM survival estimates at 48 weeks		Cox PH Model ^a	
	Placebo (n=)	Mepolizumab (n=)	HR (95% CI)	p-value
Intention to treat analysis				

a The Cox proportional hazard model will be used for the primary outcome of the time to re-hospitalisation or death (any cause) as the dependent variable. The treatment group served as an explanatory factor, while baseline MRC dyspnoea score (≤ 3 , >3) and past hospitalisation in the previous 12 months (0, ≥ 1) will be included as stratification factors.

Table 5: Protocol deviations by treatment arm and overall

	Placebo	Mepolizumab
Randomised participants		
Randomised participants with Protocol Deviations		
Participants with:		
No Protocol Deviations		
1 Protocol Deviation		
2 Protocol Deviations		
3 Protocol Deviations		
4 Protocol Deviations		
5 Protocol Deviations		
≥ 6 Protocol Deviations		

Table 5: Number of Major and Minor Protocol Deviations

	Placebo	Mepolizumab
Number of Major Protocol Deviations		
Description		
Participant ineligible for entry into Trial		
Number of Minor Protocol Deviations		
Description		
Participant ineligible for entry into Trial		
Non-compliance with treatment allocation		
Visit/assessment not performed as per Protocol		
Other		

Table 6: Number of participants with Adverse Events

	Placebo	Mepolizumab
Randomised participants		
Randomised participants with Adverse Events		
Participants with:		
No Adverse Events		
1 Adverse Event		
2 Adverse Events		
3 Adverse Events		
4 Adverse Events		
≥ 5 Adverse Events		

Figure 7: Frequency of AE term by treatment arm

Table 7: Prevalence of AEs and SAEs by relatedness and severity

	Placebo	Mepolizumab
Number of Adverse Events		
Severity		
Mild		
Moderate		
Severe		
Fatal		
Missing		
Outcome		
Resolved		
Resolved with Sequelae		
Continuing		
Fatal*		
Unknown		
Missing		
Treatment		
None		
Concomitant Medication		
Non-drug therapy		
Concomitant Medication and Non-drug therapy		
Missing		
Action taken for Adverse Event		
None		
Study interrupted		
Study discontinued		
Missing		

	Placebo	Mepolizumab
Relatedness		
	Not related	
	Unlikely	
	Possible	
	Probable	
	Definite	
	Missing	
Serious Adverse Event?		
	Yes	
	No	
	Missing	
Expectedness		
	Yes	
	No	
	Missing	

9.2 *Appendix 2: Line listing of the adverse events*

Preferred AE term	AE system	Seriousness	Start date	End date	Relatedness	Severity	Outcome	Treatment arm

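### Adverse events by term, organ class, seriousness, severity and relatedness are planned as event counts, with no number of participants affected

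*Protocol*

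**What the plan says.** Protocol 10.3 plans the breakdown by MedDRA term and class in these words: "Number and percentage of AEs will be presented for each treatment by preferred AE term and system organ class". The unit is the adverse event, and the denominator of the percentage is not given.

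SAP 3.2.1 treats adverse and serious adverse events as a count variable. SAP section 7 says that adverse event "frequencies by seriousness, relatedness and severity will be summarised by treatment group and overall", and adds frequencies by system organ class and by arm. It also plans rates per person-year, whose numerator is defined so that "Total number of events is a count of all AE/SAEs observed".

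In SAP 9.1, the shell headed "Table 7: Prevalence of AEs and SAEs by relatedness and severity" opens with a row for the number of adverse events. It then splits those events by severity, outcome, treatment, action taken, relatedness, seriousness and expectedness. Figure 7 shows the frequency of each adverse event term by arm.

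Two shells count people:
- Table 6 has a row for "Randomised participants with Adverse Events", followed by the numbers with 0, 1, 2, 3, 4 and 5 or more events.
- The disposition table (Table 1) counts deaths and reasons for stopping treatment, such as an adverse event or "Unable to Tolerate Drug".

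On the analysis set, SAP 4.5 states: "The primary analysis of safety outcomes will be analysed using the safety population".

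**The concern.** For a repeatedly injected product, a safety reader first asks what share of people on each arm had a given reaction. The planned breakdowns do not answer that. An event count mixes how many people were affected with how often each was affected. A percentage of all adverse events is no better, because it moves with the number of unrelated events on the arm.

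The protocol states its own expectation per person. Section 2.1 puts headache above 1 in 10, "followed by local injection site reactions expected in 3-8% of the population". Event counts from this trial could not be set beside those figures.

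There is also a smaller labelling point. The base row of Table 6 is randomised participants, whereas SAP 4.5 and section 7 assign safety data to the safety population.

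**Working it through.** **Step 1: the unit of each planned output**

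| Output | Unit | Split by term, class, seriousness, severity or relatedness? |
|---|---|---|
| Protocol 10.3 summary | adverse events | term and class |
| SAP 7 frequencies | adverse event frequencies | class, seriousness, relatedness, severity |
| SAP 7 rates | all events over follow-up time | no, except AEs and SAEs separately |
| Table 7 | adverse events | severity, relatedness, seriousness |
| Figure 7 | frequency of term | term |
| Table 6 | participants | no |
| Table 1 | participants | no, disposition reasons only |
| SAP 9.2 line listing | single events | listed, but the template has no participant column |

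No row combines participants as the unit with a split by these categories. Participant counts could not be rebuilt from the line-listing template either.

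**Step 2: how far events and people can diverge**

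Inputs:
- 238 randomised 1:1, so 238/2 = 119 per arm (Protocol 10.1 and 7.3).
- Up to 12 doses (Protocol 8.4), with a planned minimum of 6 under truncated follow-up (Protocol 8.4.1).
- Injection-site reactions in 3–8% of people (Protocol 2.1).
- Assumed: 6 people affected per arm, 6/119 = 5.0%, which lies inside that range. If 5% never receive a dose, as Protocol 10.1 assumes, the base is 119 × 0.95 ≈ 113 and the share is 6/113 = 5.3%.

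The comparison arm has one reaction per affected person: 6 × 1 = 6 events. On the other arm:
- two people react at all 12 doses: 2 × 12 + 4 × 1 = 28 events;
- one person does: 1 × 12 + 5 × 1 = 17 events;
- two truncated participants react at all 6 doses: 2 × 6 + 4 × 1 = 16 events.

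The participant count is 6 against 6 in every case.

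**Step 3: chance divergence when both arms behave alike**

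Both arms are given the same number of affected people and the same random repeat pattern (200,000 simulated trials, geometric draws capped at 12). The table gives the share of trials in which the larger event total is at least 1.5 times the smaller.

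| Repeat pattern | 6 affected per arm | 12 affected per arm |
|---|---|---|
| 80% once, 20% twice | 5% | 0.3% |
| Geometric, mean 1.5 | 24% | 9% |
| Geometric, mean 2 | 34% | 17% |
| 90% once, 10% at all 12 doses | 58% | 50% |

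Twelve per arm corresponds to about 10% of 119, close to the level the protocol gives for headache. The participant counts are equal throughout.

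**The case against.** The strongest reply is that the SAP's wording is loose rather than wrong. Section 7 says frequencies without naming a unit, and the title of Table 7 speaks of prevalence, which can mean people. The lead row of Table 7 does point to events, but that shell has no rows for term or organ class. This has some force. However, the protocol's wording, the count-variable definition and the Table 7 lead row all point to events, and nothing names participants as the unit for these categories. If participants were intended, the same edit is needed to say so.

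Other points on that side:
- **Fatal events.** The fatal rows in Table 7 are in effect participant counts, since a person dies once. That is true, but it helps no other category.
- **Table 6.** It does show who had many events, so a 12-time reactor would fall in the row for 5 or more. It does not show which event recurred.
- **Anaphylaxis and major cardiac events.** Protocol 2.1 commits to analysing these. That covers two event types, and neither SAP section 7 nor the shells has a matching output.
- **The illustration.** The documents give no repeat rate, and the result depends on the assumed pattern. It also assumes that each recurrence is recorded as a new event. Stopping treatment after a reaction would reduce repeats, and the effect falls for commoner events. All of this stands, so the numbers show what is possible and are not a forecast.
- **It could be added later.** The records would allow it, but Protocol 10.9 requires analyses beyond the SAP to be reported as unplanned.

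**Conclusion.** The concern holds. The planned breakdowns by preferred term, system organ class, seriousness, severity and relatedness count events, and no planned output gives the number and percentage of participants with at least one event in these categories, apart from the trivial case of fatal events.

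The size cannot be fixed from the documents, because it depends on how often reactions recur in the same person and on how recurrences are recorded. With 6 people affected per arm, an imbalance of 1.5-fold or more in events would arise by chance in 5% to 58% of trials across the patterns tabulated. With 12 affected per arm the range is 0.3% to 50%.

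Safety is summarised descriptively, so no planned test or efficacy estimate changes. This is a gap in the pre-specified display, worth closing because it is cheap. The Table 6 base is a label correction.

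**What to change.** In SAP section 7 and the shells in 9.1, add by arm the n (%) of safety-population participants with at least one event:
- by preferred term within system organ class;
- by seriousness, worst severity and relatedness.

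Count each participant once per category and use the number in the safety population on that arm as the denominator. Keep the planned event counts and rates beside these figures, since they show recurrence. State the unit explicitly wherever the SAP now says frequency or prevalence. Relabel the base of Table 6 as the safety population, in line with SAP 4.5 and section 7.

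The cost is revised shells and slightly longer tables. The same adverse event records are used and no new data are needed.
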